4.1 Primary and secondary endpoint

CR (primary end point, *i.e.* conversion from being egg positive pre-treatment to egg negative post-treatment) and ERR (secondary end point). In addition, diagnostic performance using different tools will be evaluated, *Trichuris* strains described using molecular characterization and safety and potential benefits on morbidity indicators from treatment assessed (secondary end points).

4.2 Type of trial

Double blind randomized controlled trial.

Page 64 of 176

4.3 Trial design

4.3.1 Baseline survey and screening

A randomized-controlled trial will be conducted with two treatment arms to be followed-up over a 12 months period with an intermediate re-treatment of participants found re-infected after 6 months (Figure). This trial will be conducted as a multi-country study; thus, in each setting a separate trial according to the design described below will be set up, to provide a better basis for the subsequent generalization of its findings. This arises from the possibility of recruiting the subjects from a wider population and of administering the medication in a broader range of clinical settings, thus presenting an experimental situation that is more typical of future use. The study includes one baseline and three follow-up assessments at 3 weeks (day 21), 6 months (day 180), and 12 months (day 360).

Figure 1. Design and timeline of the randomized-controlled trial to be implemented in each of three settings.

The study is designed as a two-armed trial including one arm with a single drug administration (arm A; albendazole) and one arm with combined treatment through co-administration of separate tablets (arm B; albendazole and ivermectin).

The trial will be conducted as a multi-country study with two settings in Africa and one in Asia, namely Côte d'Ivoire, Pemba (Zanzibar, Tanzania) and Lao PDR.

At baseline, all participants will be asked to provide two stool samples (within a maximum of 5 days). From each stool specimen, duplicate Kato-Katz thick smears (41.7 mg each) [16] will be prepared and read under a

Page 65 of 176

microscope for eggs of T. trichiura, A. lumbricoides and hookworm by experienced technicians and a subsequent independent quality control of sample results (approximately 10%) will be conducted. Results are considered correct if the following tolerance margin is not exceeded: (i) No difference in presence/absence of hookworm, A. *lumbricoides* and *T. trichiura*, (ii) egg counts are +/-10 eggs for counts ≤ 100 eggs or +/-20% for counts >100eggs (for each species separately) [17]. In case discrepancies above the tolerance margin are noted in one or more slides, all slides are re-read by the local technicians. The new results are discussed, so that in case of discordant results, slides can be re-evaluated to reach consensus. Infection intensity expressed as the arithmetic and geometric mean egg count per gram of stool (EPG) will be calculated for each treatment arm. All microscopically analyzed quadruplicate Kato-Katz thick smears will be destroyed within one day (after passing the quality control). S. stercoralis infections will be identified using the Baermann technique. Additionally, a portion of 1.5-2 g of stool from each specimen will be preserved in 70% ethanol and shipped to a reference laboratory for polymerase chain reaction (PCR) analysis [18]. PCR will allow to accurately determining efficacy and for further classification of hookworm infection into the three species N. americanus, A. duodenale and A. ceylanicum. From a subsample of 10 children with heavy intensity infections an additional portion of stool (1.5-2 g) will be preserved in 95% ethanol, shipped to a reference laboratory and subjected to whole genome sequencing for characterization of Trichuris strains. Each collected stool sample will further be tested on fecal occult blood and calprotectin as proxies for gut morbidity and inflammation using a rapid diagnostic test and an immunoassay, respectively [19]. The same sampling procedure and diagnostic approach will be applied at days 21, 180 and 360 post-treatment.

Patients with filarial disease showed significantly higher numbers of adverse events (AEs) for treatment with ivermectin in combination with albendazole in earlier studies [20-22]. A rapid diagnostic test (RDT; i.e., SD BIOLINE Oncho/LF IgG₄ biplex test) to detect antigens in the blood will therefore be used to identify potential co-infection with *Wuchereria bancrofti*.

A clinical examination of the study participants assessing general health, anthropometric parameters including height, weight, mid-upper arm circumference (MUAC) and triceps skinfold thickness as well as tympanic temperature using an ear thermometer will precede the treatment and will be repeated on two follow-up assessments (days 180 and 360) to evaluate potential benefits from deworming. Each participant will be asked to provide a finger-prick blood sample to evaluate hemoglobin (Hb) levels using a HemoCue analyzer (Hemocue Hb 301 system; Angelholm, Sweden) following the same (re-)assessment schedule. To avoid accidental treatment of pregnant girls/women all female participants (≥ 10 years) will be asked to provide a urine sample to be subjected to a pregnancy RDT on day 0 and day 180.

All trial participants will further be asked about existing clinical symptoms before drug administration. Additionally, they will be asked to provide subjective short-term (e.g. convenience of treatment) and long-term (e.g. effectiveness in reducing symptoms) treatment satisfaction embedded in the re-assessment questionnaires. As a measure of patient-rated physical functioning and wellbeing all children (6-16 years) will be administered a questionnaire before, 6 and 12 months after treatment, based and adapted from tools already validated in schoolaged children from rural settings in Côte d'Ivoire [23]. Before application this tool will be adapted to local conditions of Pemba and pre-tested in a comparable school-aged population not otherwise involved in this trial. To adjust for known influencing factors with regard to reinfection and morbidity [24, 25] in the subsequent analysis and to identify risk factors for residual infections [26] a household-based questionnaire will be administered to one adult member of each participating household, assessing information on socioeconomic characteristics, access to sanitation and water facilities as well as hygiene behavior.

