4.3.2 Assessment of efficacy after treatment

The efficacy of the treatment will be determined 21 days post-treatment by collecting another two stool samples which will be microscopically examined for *T. trichiura* using duplicate Kato-Katz thick smears and potential co-infection with *S. stercoralis* applying the Baermann technique. Participants will be considered *T. trichiura* cured if no eggs have been found in the stool. EPG will be assessed by adding up the egg counts from the quadruplicate Kato-Katz thick smears and multiplying this number by a factor of six. Geometric and arithmetic mean egg counts will be calculated for the different treatment arms before and after treatment to assess the

corresponding ERRs. The stool samples collected 21 days post-treatment for efficacy assessment will further be re-tested with the same rapid diagnostic test and immunoassay used at baseline to determine fecal occult blood and calprotectin levels. Frequencies of subjects found positive with either of the two markers and by intensity category for calprotectin will be calculated by treatment arm.

At the end of the study (approximately 12 months post-treatment) all participants remaining positive for *T*. *trichiura* and other soil-transmitted helminths will be treated with albendazole-ivermectin, the currently best recommended treatment against *T*. *trichiura*.

Potential extended effects on follow-up helminth prevalences will be assessed using the same methodological approach as used for the efficacy assessment and will be based on stool samples collected 6 and 12 months post-treatment. Likewise fecal occult blood and calprotectin will be re-determined on the same stool samples.

To assess eventual reduction in morbidity indicators all trial participants will be asked to provide another fingerprick blood sample at the 6 and 12 month follow-up for Hb measurement. Anthropometric measurement including height, weight, MUAC and triceps skinfold thickness will be repeated on the same occasion. Children (6-16 years) will be asked to re-assess their own physical functioning in repeated questionnaire interviews during these two last follow-ups. Long-term satisfaction with the treatment will be asked 6 months past-treatment. Mean values for continuous outcomes and frequencies for binary/categorical outcomes will be calculated for each treatment arm and follow-up time point and compared using descriptive and repeated measurement analysis as detailed in section 7.3.

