5.3 Exclusion criteria

- 1. No written informed consent by individual/parents and/or caregiver.
- 2. Presence of major systemic illnesses, e.g., severe anaemia (below 80 g/l Hb according to WHO)[27], as assessed by a medical doctor, upon initial clinical assessment.
- 3. History of acute or severe chronic disease (e.g. cancer, diabetes, chronic heart, liver or renal disease).
- 4. Recent use of anthelmintic drug (within past 4 weeks).
- 5. Attending other clinical trials during the study.
- 6. Negative or low egg count (less than 100 EPG or less than 2 out of 4 slides positive) diagnostic result for *T. trichiura* eggs in the stool.
- 7. Pregnancy or lactating in the 1st week after birth (according to WHO guidelines within LF control programs [28]).
- 8. Known allergy to study medications (*i.e.* albendazole and ivermectin).

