To avoid interference of potential on-going control programs against helminthiases with the infection status of the trial participants, communication with local stakeholders will be established to ascertain that trial participants will not undergo MDA treatment. Missed-out rounds of planned MDA against STH in the participating study communities be substituted with a free community-wide single-dose treatment (i.e., albendazole 400 mg + ivermectin 200 μ g/kg) against STH as well as *S. stercoralis* infection at the study endpoint (after the day 360 follow-up assessment) offered by the study team. At each follow-up time point, participants will be interviewed whether they had taken anthelmintic treatment (e.g. self-purchased, obtained from clinics etc). Participants found to be severely anemic at any of the three assessment time points (baseline, 6 and 12 months post-treatment) will be referred to the next hospital/clinic.

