7.2 Justification of number of trial subjects

Based on available summarized efficacy measures from a recent review [1] and the published literature, we assume that the CR of albendazole against *T. trichiura* is 30% compared to 50% in the albendazole-ivermectin treatment regimen. To detect a difference with 90% power at a two-sided 5% significance level, we require 121 participants per study arm and 143 to account for potential loss to follow-up of 15%. We further assume the same treatment efficacy in the mid-term treatment and a 6-months reinfection risk of 10%. Consequently we expect a proportion of negative patients after 12 months of 44% in the albendazole arm and of 65% in the albendazole-ivermectin arm resulting in a required sample size of 111 participants per arm. To account for a loss to follow-up of 30% after 6 months and 40% at final assessment (12 months) we aim to recruit 300 participants in each group (600 in total). This number is largely sufficient to further show differences in efficacy in subgroups such as school-aged versus adult study populations without losing statistical power as long as individuals get recruited in similar proportions to these two groups.

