A clinical examination of the study participants assessing general health, anthropometric parameters including height, weight, mid-upper arm circumference (MUAC) and skinfold thickness (i.e. triceps and subscapular skinfolds) as well as tympanic temperature using an ear thermometer will precede the treatment and will be repeated on two follow-up assessments (days 180 and 360) to evaluate potential benefits from deworming. Each participant will be asked to provide a finger-prick blood sample for a RDT for *Plasmodium* spp. infection and to evaluate hemoglobin (Hb) levels using a HemoCue analyzer (Hemocue Hb 301 system; Angelholm, Sweden) following the same (re-)assessment schedule. To assess potential improvement on nutritional indicators for micro- (*i.e.* (pro-) vitamins, inflammation markers, and iron/ferritin) and macronutrient (*i.e.* albumin) deficiencies and dynamics of biochemical blood parameters as a proxy for functioning of vital organs a venous blood sample (approximately 8 ml) will be taken at baseline, day 21, day 180 and 360. The biochemical parameters to be assessed include urea, creatinine, bilirubin, azotemia, Alanine Amino Transferase (ALAT), Aspartate Amino Transferase (ASAT) as well as blood cell counts (*e.g.* hematocrit, erythrocytes and platelets). To avoid accidental treatment of pregnant girls/women all female participants (\geq 10 years) will be asked to provide a urine sample of at least 10 ml to be subjected to a pregnancy RDT on day 0 and day 180.

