4.3.2 Assessment of efficacy and other benefits after treatment

Parallel group multi-country and DF study

The efficacy of the treatment will be determined 21 days post-treatment by collecting another two stool samples which will be microscopically examined for *T. trichiura* using duplicate Kato-Katz thick smears and potential co-infection with *S. stercoralis* applying the Baermann technique. Participants will be considered *T. trichiura* cured if no eggs have been found in the stool. EPG will be assessed by adding up the egg counts from the quadruplicate Kato-Katz thick smears and multiplying this number by a factor of six. Geometric and arithmetic mean egg counts will be calculated for the different treatment arms before and after treatment to assess the corresponding ERRs. The stool samples collected 21 days post-treatment for efficacy assessment will further be re-tested with the same rapid diagnostic test and immunoassay used at baseline to determine fecal occult blood and calprotectin levels. Frequencies of subjects found positive with either of the two markers and by intensity category for calprotectin will be calculated by treatment arm.

At the end of the study (*i.e.* for exclusive DF study participants 1 month post-treatment, for trial participants 12 months post-treatment) all participants remaining positive for *T. trichiura*, other soil-transmitted helminths or filariasis will be treated with albendazole-ivermectin, the currently best approved and recommended treatment against *T. trichiura* [29].

Page 107 of 176

Parallel group multi-country study

Potential extended effects on follow-up helminth prevalences will be assessed using the same methodological approach as used for the efficacy assessment and will be based on stool samples collected 6 and 12 months post-treatment. Likewise fecal occult blood and calprotectin will be re-determined on the same stool samples.

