To avoid interference of potential on-going control programs against helminthiases with the infection status of the trial participants, communication with local stakeholders will be established to ascertain that trial participants will not undergo MDA treatment. Missed-out rounds of planned MDA against helminthiases in study participants will be substituted with a free single-dose treatment (*i.e.* albendazole 400 mg + ivermectin 200 μ g/kg) against STH, *S. stercoralis* as well as *Filaria* infection at the study endpoint (after the day 360 follow-up assessment) offered by the study team. At each follow-up time point, participants will be interviewed whether they had taken any anthelmintic treatment (e.g. self-purchased, obtained from clinics etc).

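### No pregnancy test is scheduled before the end-of-study albendazole-ivermectin dose at about 12 months, although testing precedes the two earlier doses

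*Combined protocol and SAP*

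**What the plan says.** **Testing.** Section 4.3.1 of the Swiss-approved, Pemba and Côte d'Ivoire protocols gives the purpose of the urine test as preventing accidental treatment in pregnancy. In Pemba, female participants aged 10 or over "will be asked to provide a urine sample to be subjected to a pregnancy RDT on day 0 and day 180". The Côte d'Ivoire urine sample is likewise "to be subjected to a pregnancy RDT on day 0 and day 180". The Laos sentence is damaged in the extracted text, but its test days can be read and are the same. In the schedules of visits (section 4.6 of each protocol) the pregnancy row is marked at hour 0 and day 180 and is blank at day 360. The SAP's Time and Events Table agrees.

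**End-of-study dose.** Section 4.3.2 of the Pemba and Laos protocols reads "At the end of the study (approximately 12 months post-treatment) all participants remaining positive for" *T. trichiura* and other soil-transmitted helminths will receive albendazole-ivermectin. The Swiss-approved and Côte d'Ivoire texts say the same "for trial participants 12 months post-treatment) all participants remaining positive for" these infections, and add filariasis.

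**Replacement of missed mass drug administration (MDA).** Under section 5.5, missed rounds in Pemba are to be "substituted with a free community-wide single-dose treatment" of the same combination. The Laos and Côte d'Ivoire protocols offer it to study participants against *S. stercoralis*, among others: "infection at the study endpoint (after the day 360 follow-up assessment) offered by the study team".

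**Exclusion.** "Pregnancy or lactating in the 1st week after birth" appears in section 5.3 as a criterion for entering the trial.

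**The concern.** The sponsor names a hazard, chooses a control, and applies it before two of the three planned dosing occasions. The day 180 test immediately precedes the day 185 re-treatment, so the plan itself does not accept the entry exclusion, or a six-month-old negative result, as sufficient before dosing again. At the third occasion the same situation returns without the control. A negative result at day 180 says nothing about conception since then.

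The third dose also differs from the second in one respect that matters. Re-treatment at day 185 follows the allocated arm, whereas the end-of-study dose gives ivermectin to positives from both arms, including those previously allocated albendazole alone.

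Nor would a consequence be picked up later. Adverse events are observed to day 21 after treatment, the schedules mark no adverse event capture at day 360, and section 6.1.4 declares congenital anomaly irrelevant to the study.

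**Working it through.** **1. Latest scheduled test before each dose**

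| Dose | Recipients | Latest scheduled test | Age of test |
|---|---|---|---|
| Day 0 | All randomised | Day 0 | 0 days |
| Day 185 | Positive at 6 months | Day 180 | 185 − 180 = 5 days |
| About day 360 | All still positive, plus MDA replacement | Day 180 | 360 − 180 = 180 days |
| About day 360, day 180 visit missed | As above | Day 0 | 360 − 0 = 360 days |

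Each follow-up round lasts about three weeks (section 4.5), so these intervals are approximate.

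**2. Other provisions that might close the gap**

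- The section 5.3 exclusion operates at enrolment, a year earlier.
- The day 360 clinical examination covers general health, anthropometry and temperature, and is repeated to look for gains from deworming. No pregnancy assessment is named.
- Laos collects urine at day 360, but for *S. stercoralis* antibodies.
- Laos section 9.2 refers to national recommendations for treating remaining positives, without naming a check.
- Section 8.3 lets investigators take protective steps, but schedules none.
- The data list in section 7.4 of the Swiss-approved, Côte d'Ivoire and Laos protocols includes pregnancy among the recorded characteristics, with no day given.

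**3. How many participants would be due the dose**

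The input is section 7.2: "we expect a proportion of negative patients after 12 months of 44% in the albendazole arm and of 65" (the last figure being a percentage, for the combination arm). Both figures follow from the plan's assumed cure rates of 30% and 50%, the same cure rates at re-treatment, and 10% reinfection per six months:

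- Albendazole: (0.30 × 0.90 + 0.73 × 0.30) × 0.90 = (0.270 + 0.219) × 0.90 = 0.440
- Combination: (0.50 × 0.90 + 0.55 × 0.50) × 0.90 = (0.450 + 0.275) × 0.90 = 0.653

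Here 0.73 = 1 − 0.27 and 0.55 = 1 − 0.45 are the proportions positive, and so re-treated, at six months.

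With 300 per arm per country and 40% lost by 12 months:

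- Seen at day 360, per arm and country: 300 × 0.60 = 180
- Positive per country: 180 × (1 − 0.44) + 180 × (1 − 0.65) = 100.8 + 63.0 = 163.8, about 164
- Three countries: 3 × 163.8 = 491.4, about 491
- With no loss: 900 × 0.56 + 900 × 0.35 = 504 + 315 = 819

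Positives for other helminths and accepted MDA replacement doses come on top. The count covers both sexes and ages 6-60. The documents give neither the share of females of testing age nor a pregnancy frequency. Purely as illustration, each 10 percentage points of such females among the 491 is 0.10 × 491, or about 49 people dosed without a current test.

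**The case against.** The best contrary case is that the evidence is silence about a treatment given as the study closes. The visit schedule has a column for day 185 re-treatment but none for the end-of-study dose, so an empty day 360 cell proves little by itself. Standard operating procedures are mentioned but not supplied, and the consent pages were removed, so a check could be described there. The exclusion criterion cites WHO guidance for filariasis programmes, and the MDA replacement stands in for programme rounds whose usual practice might cover pregnancy. The text printed as the Côte d'Ivoire protocol carries version 1.01 of 12.06.2018 and still contains the dose-finding study, whereas the SAP cites version 1.03 of 22.11.2018. Finally, 491 does not measure exposed pregnancies.

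Some of this stands. The finding is limited to the text as supplied. Evidence for Côte d'Ivoire is weaker, although that text was supplied as final and the change history lists no alteration to pregnancy testing. The 491 is a count of all treated positives and nothing more. None of it supplies a check. Sections 4.3.2 and 5.5 prescribe or offer the dose themselves, through the study team, so leaving it out of the table does not put it outside the protocol. Unseen documents cannot be assumed to repair a gap in the protocol's own dosing instructions.

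**Conclusion.** The concern holds. In all four printed protocols, following the instructions as written means giving albendazole-ivermectin at about 12 months on the strength of a pregnancy test about 180 days old, or about 360 days old where the day 180 visit was missed. That defeats the stated aim of the testing.

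On the planning assumptions (44% and 65% negative, 40% lost), about 491 *T. trichiura* positives are due this dose, and 819 with no loss. How many are women who could be pregnant is unknown. In Pemba the community-wide replacement dose can also reach women the study never tested.

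This is a matter of participant safety and should be corrected. It has no bearing on the day 14-21 cure-rate comparison.

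**What to change.** 1. In section 4.3.1 and the schedule of visits of each protocol, add the existing urine pregnancy test at day 360, before any end-of-study dose, for female participants of testing age. That age is 10 years and over, except in Laos, where the Supplement overview says 12 but section 7.4 still says 10; the amendment should state one figure.
2. In sections 4.3.2 and 5.5, state that girls and women who are pregnant or in the first week of lactation are not dosed then, but deferred or referred.
3. In Pemba section 5.5, state how pregnancy is checked among non-participants offered the community-wide dose. Items 1 and 2 are worth making even if this is handled separately.

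A secondary tidy-up would be to drop the remark in section 6.1.4 that congenital anomaly is irrelevant. It has little effect unless exposed pregnancies are also followed beyond the serious adverse event window (day 21; 24 hours in Pemba).

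The cost is a few lines of text and test kits at a visit already planned; Laos already collects urine then. Some women would receive their end-of-study treatment later.
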